9.0 STATISTICAL ANALYSIS PLAN

Data Protection and Confidentiality

We will have two independent phase I 3x3 escalations going on simultaneously, one for LS-SCLC patient in part A (with chemotherapy) and those for ES-SCLC (without chemotherapy) for part B.

All patients who meet eligibility criteria and are enrolled in this trial will be registered in Clinical Oncology Research Database (CORE) at the University of Texas M D Anderson Cancer Center at Houston. All protocol participants must be registered in the CORE. The date in the current informed consent document is displayed to ensure only the most current IRB approved version is used. Consent date, registration date, off study date, and evaluability data are required for all registrants.

The principal investigator agrees to keep all information and results concerning the study confidential. The confidentiality obligation applies to all personnel involved with this clinical trial. The Investigator must ensure that each participant's anonymity will be maintained in accordance with applicable laws. The principal investigator should keep a separate log of ID numbers, names and addresses. Documents that contain the names associated with these ID numbers (e.g., written consent/assent forms), should be maintained by the Investigator in strict confidence except to the extent necessary to allow auditing by regulatory authorities, auditing or monitoring by the IRB.

The Principal Investigator shall obtain all such permissions and authorizations as may be necessary or desirable to allow the collection and use of information protected under federal privacy laws and state privacy laws, including permission/authorization for monitoring and analysis (including

re-analysis in combination with results of other studies), for regulatory submission purposes and for applicable reporting (if any).

[figure not shown]
Under this protocol, we will collaborate with [name] at the University of Nebraska. All data sent to [name] will be de-identified with no names, dates, or medical record numbers. The de-identified data will be sent in an Excel spreadsheet via MDACC encrypted email and will be used to perform analysis. Patient identification information will be removed from all documents. The data will be coded by anonymous study numbers using a key kept separate from the database that only the principal investigator will have access to. Data will be stored on a password and firewall protected computer.

9.1 Data Set Descriptions

This study will utilize a standard 3+3 design and dose de-escalation will proceed according to the following scheme. Three doses of MK-3475 (100 mg, 150 mg, 200 mg) will be given to 3 different groups of 3 patients. If the toxicity is greater than 1/3 in one group then the next lower dose will be used. This will establish the MTD, if present. If more than 1/3 of patients experience DLTs at the lowest dose (70 mg), it will be concluded that MK-3475 cannot be given safely with chemo/radiation. If one of three patients at any dose level experiences grade 3 or greater toxicity then another 3 patient will be accrued at the same dose level. If 1/6 patients has grade 3 or higher toxicity then escalation will proceed, if 2/6 has grade 3 or greater toxicity then this is declared the MTD. If 3/6 has grade 3 or greater then we will reduce the dose level.

Part A: Is only for patients with Limited stage SCLC, we will allow induction chemotherapy.

Part A for LS-SCLC

Part B: Is only for patients with Extensive stage SCLC who are receiving consolidation XRT after 1-6 cycles of chemotherapy.

[figure not shown]

Table 1: Dose De-escalation, For Part A and B

Dose Level	MK-3475 (dose during XRT)	Toxicity Assessment	New MK 3475 dose
+2	200mg Q 3 weeks	If over 1/3 grade 3 toxicity is seen	150mg Q 3 weeks
+1	150mg Q 3 weeks	If over 1/3 grade 3 toxicity is seen If 0/3 grade 3 toxicity is seen	100mg Q 3 weeks 200mg Q 3 weeks
0 (starting dose)	100mg Q 3 weeks	If over 1/3 grade 3 toxicity is seen If 0/3 grade 3 toxicity is seen	70mg Q 3 weeks 150mg Q3 weeks
-1	70mg Q 3 weeks	If over 1/3 grade 3 toxicity is seen	We will conclude MK-3475 cannot be safely given after Chemo/radiation

Once the MTD is determined for each study part we will accrue at this MTD until we reach a total of 40 patients for each study part. Should DLTs occur in more than 1/3 of patients enrolled into this expanded cohort, dosing at that level will be stopped. A review of all DLTs observed will be conducted, and the need to lower the dose will be based on the discussion and agreement between

the IRB and the Investigator. Once at dose level +2, if 0/3 toxicity is seen we will not close the study for new patient enrollment until the third patient has passed the DLT assessment period, because even if this third patient has a DLT was seen it would no change the dose for future patients as another 3 patients at the same dose level would be needed.

All patients who receive any MK-3475 will be considered evaluable for response and will be included in the efficacy data set.

DLT is defined as any:

- DLTs are defined as any adverse event(s) considered related to the combination of MK-3475 plus radiation as described below:
 - Any \geq Grade 3 bronchospasm or other hypersensitivity reaction;
 - Any other \geq Grade 3 non-skin related adverse event with the exception of laboratory abnormalities;
 - Any Grade 4 laboratory abnormalities, except AST, ALT, or total bilirubin;
 - AST or ALT $> 8 \times$ ULN,
 - Total bilirubin $> 5 \times$ ULN;
 - Any other Grade 4 adverse event;
- 1. Any adverse event, laboratory abnormality or intercurrent illness which, in the judgment of the investigator, presents a substantial clinical risk to the subject with continued study drug dosing;
- 2. Subject experiences an allergic/infusion reaction while receiving study drug at a slower infusion rate due to a prior allergic/infusion reaction;
- 3. Any motor neurologic toxicity \geq Grade 3 regardless of causality;
- 4. Any \geq Grade 3 treatment-related sensory neurologic toxicity.
- 5. Drug related toxicity that prevents administration of MK-3475 for > 21 days from the scheduled dose
 - The time frame for DLT assessment will be within 22 days of therapy initiation.
 - Any grade 4 neutropenia (with or without fever and/or sepsis) or thrombocytopenia (with or without bleeding) lasting at least 1 week or longer (as defined by the NCI-CTC v4.0).
 - Any other grade 3 non-hematologic toxicity including symptoms/signs of vascular leak or cytokine release syndrome; or any severe or life-threatening complication or abnormality not defined in the NCI-CTCAE v4.0 that is attributable to the therapy.

9.2.1. *Statistical Analysis*

Descriptive statistics will be computed for all relevant outcomes, including toxicity, tumor response, PFS, OS, and biomarker response. Descriptive analysis will include a global assessment of patient outcomes for parts A and B separately. All patients receiving at least 1 treatment with MK-3475 will be included in the analysis.

9.2.2. *Demographics and Baseline Characteristics*

Frequency distributions of gender and race will be tabulated by dose/cohort. Summary statistics for age, body weight, height, and Body Mass Index (BMI) will be tabulated by dose/cohort.

9.2.3. *Safety Analyses*

All recorded adverse events will be recorded per MDACC guidelines using CTCAE Version 4.0. Frequency of adverse events will be tabulated by grade, type, and dose/cohort. Relative frequencies and confidence intervals will also be constructed.

9.2.4. *Efficacy Analyses*

Efficacy data from part A and part B will be performed using the criteria below.

1. **Global irRC:** irRC that factors all lesions both index and non-index.
2. **In-Field irRC:** irRC in which only XRT-treated lesions will be considered and non-index lesions arising inside the XRT PTV
3. **Out-Field irRC:** irRC in which only non XRT-treated lesions will be considered and non-index lesions arising outside the XRT PTV

Time-to-event distributions for PFS and OS will be estimated via Kaplan-Meier analysis. Summary statistics will be computed along with confidence intervals. The limited sample size precludes formal statistical comparison with historical controls.

9.2.5. *Sample Size/Accrual Rate*

The maximum planned number of patients will be 80, with 40 patients being treated with LS-SCLC and 40 patients with ES-SCLC. It is estimated that approximately 1.5 patients per month (for both LS-SCLC and ES-SCLC) will be accrued over 26 months. With 40 patients, the probability of seeing at least one patient with toxicity if the true toxicity rate is 0.1 is 88%. The 95% binomial confidence interval for 6/20 (30%) extends from 15% to 52%.

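### Section 9.1 runs its 3+3 rules on grade 3 toxicity in some places and on DLTs in others without equating them, and the DLT list has two loose ends of its own (skin events and item 5).

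*Combined protocol and SAP*

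**What the plan says.** Section 9.1 states: "This study will utilize a standard 3+3 design". Its dose rules then name two different events.

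- **Grade 3 toxicity.** The rule that adds three patients reads "If one of three patients at any dose level experiences grade 3 or greater toxicity". The 1/6, 2/6 and 3/6 outcomes use the same event. Table 1 gives the condition for lowering the dose, or at 70 mg for stopping, as "If over 1/3 grade 3 toxicity is seen". None of these rules states an attribution or a time window.
- **DLT.** The 70 mg stop in the prose begins "If more than 1/3 of patients experience DLTs at the lowest dose (70 mg". The dose level +2 sentence says that "even if this third patient has a DLT was seen it would no change the dose for future patients", because another three patients would be needed. The expansion rule is "Should DLTs occur in more than 1/3 of patients enrolled into this expanded cohort, dosing at that level will be stopped".

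The 70 mg stop therefore appears both ways: DLTs in the prose, grade 3 toxicity in Table 1.

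The definition that follows says "DLTs are defined as any adverse event(s) considered related to the combination of MK-3475 plus radiation". Its main grade 3 bullet leaves out skin events and laboratory abnormalities. Laboratory events count from grade 4, with separate limits for AST/ALT (above 8 x ULN) and bilirubin (above 5 x ULN). Assessment is within 22 days of starting therapy. Item 1 lets the investigator add any event that "presents a substantial clinical risk to the subject with continued study drug dosing". Item 5 adds drug-related toxicity that prevents MK-3475 for more than 21 days from the scheduled dose. The last bullet adds any other grade 3 non-hematologic toxicity.

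**The concern.** Section 4.2.3.1 makes safety, in order to establish the MTD, the primary endpoint of both parts. The 3+3 count produces that result, so the counted event has to be the same wherever the rule appears. Here the table that staff would consult at a cohort decision names a different event from the DLT definition.

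The gap is easiest to see in Part A, where platinum and etoposide are given with MK-3475. Section 5.2.1.2 does not hold MK-3475 for grade 3 hematologic toxicity, yet a literal reading of Table 1 could lower the dose for the next patients because of it. Two escalations run at the same time, which gives further room for the rule to be applied unevenly.

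Reading every rule as DLT does not settle everything, because the DLT list is itself unclear on grade 3 skin events and on the timing of item 5.

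**Working it through.** **1. Which events fall in the gap**

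| Event | Literal grade 3 rule | DLT list |
|---|---|---|
| Grade 3 event from chemotherapy only (Part A) | counts | generally not: not related to MK-3475 plus radiation |
| Grade 3 laboratory abnormality (both parts) | counts | not under the main bullet; subject to item 1 and the last bullet |
| Grade 3 event after day 22 (both parts) | counts | outside the window |
| Grade 3 skin event (both parts) | counts | left out by one bullet, readmitted by the last |
| Lower-grade event under item 1, 2 or 5 | does not count | counts; these items set no grade |

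**2. Worked case.** Part A at 100 mg: three patients, no DLT, two with chemotherapy-only grade 3 neutropenia. The DLT count is 0/3, so the next dose is 150 mg. The literal count is 2/3, which is over 1/3, so the next dose is 70 mg.

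**3. Size.** The documents give no rates for these events, so the following are assumptions. Each patient independently has a DLT (probability a), only a non-DLT grade 3 event (b), or neither (1 - a - b). Every DLT is taken as grade 3 or higher. The Section 9.1 rules are:

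- 0/3: escalate. 1/3: add three. 2/3 or more: reduce.
- 1/6: escalate. 2/6: MTD. 3/6 or more: reduce.

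With p the probability of a counted event, P(escalate) = (1-p)^3 + 3p(1-p)^2 x (1-p)^3.

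- DLT reading, p = a = 0.10: 0.729 + 0.243 x 0.729 = 0.906.
- Literal reading, p = a + b = 0.20: 0.512 + 0.384 x 0.512 = 0.709.

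Applying both readings to the same patients over all 3^6 = 729 sequences gives the probability of different decisions:

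| a | b=0.01 | b=0.02 | b=0.05 | b=0.10 | b=0.20 |
|---|---|---|---|---|---|
| 0.05 | 0.012 | 0.024 | 0.071 | 0.166 | 0.385 |
| 0.10 | 0.019 | 0.040 | 0.104 | 0.220 | 0.449 |
| 0.20 | 0.029 | 0.058 | 0.142 | 0.275 | 0.500 |

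At a = 0.10, the literal reading escalates with probability 0.889, 0.871, 0.814, 0.709 and 0.494 across those values of b, against 0.906 on DLTs. The decisions are opposite (escalate against reduce) with probability 0.087 at b = 0.10 and 0.239 at b = 0.20. The literal reading is never the laxer one here, but only because the model has no DLT below grade 3.

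**4. Skin events.** One bullet limits grade 3 DLTs to events that are not skin related. The last bullet takes in any other grade 3 non-hematologic toxicity, and a grade 3 rash is one. The list does not say which bullet prevails.

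**5. Item 5.** Take day 1 as the first MK-3475 dose. Dosing is every 3 weeks (Table 2), so dose 2 is due on day 1 + 21 = 22. A delay of more than 21 days is known only after day 22 + 21 = 43, about three weeks after the window closes. This applies to a temporary hold. A decision to discontinue permanently is known when it is made.

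**The case against.** The strongest reply is that the intent is clear. Section 9.1 calls the design a standard 3+3. The dose level +2 sentence applies the one-in-three rule to a DLT and refers to the DLT assessment period. The 70 mg stop reaches one conclusion in both vocabularies, which suggests that the terms were used as synonyms. This largely stands: DLT is very probably meant. A reader might infer that the trial would in fact escalate on all grade 3 events; the documents do not support that. What remains is that the intent must be inferred, against the wording of every row of Table 1.

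Three other strong readings also go too far.

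- *The gap belongs to Part A.* Chemotherapy-only events arise there, but laboratory events and events after day 22 fall in the gap in Part B too, and no rates are given by which to rank the parts.
- *Item 5 can never be met in time.* Permanent discontinuation, for example for grade 3 pneumonitis under Section 5.6.1.2, is known at once. Counting by onset is a natural reading, though an unstated one.
- *The last bullet overrides the liver limits.* This is only arguable. It joins a dose-hold sentence in Section 5.2.1.2 to the grade 3 values in Appendix 13.4 (AST/ALT above 5.0 and bilirubin above 3.0 x ULN), and any other may simply mean events not already covered. The skin conflict is the firmer one.

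Finally, the probabilities rest on assumed rates. That is correct, and the inconsistency in the text does not depend on them.

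**Conclusion.** The point holds as a defect of wording in the rule that determines the MTD. Section 9.1 names two non-identical events and never equates them in the text available. The 70 mg stop is worded both ways, and the same three patients can lead to 150 mg or 70 mg. The DLT list is also unclear on grade 3 skin events and, for a temporary hold of dose 2, on item 5.

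Under the model, disagreement runs from about 1% to 50% of cohorts as b goes from 0.01 to 0.20 and a from 0.05 to 0.20. At b of 0.02 or less it is at most about 6%. It should be fixed because the change is cheap and the rule drives the primary result. There is no evidence that cohorts were or would be misassigned.

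**What to change.** Amend Section 9.1 only:

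1. In the prose and Table 1, replace grade 3 (or greater, or higher) toxicity with DLT as defined in that section.
2. Limit the last DLT bullet to events not already addressed by the skin and laboratory bullets.
3. State that item 5 counts when the causative toxicity began inside the 22-day window, even if the delay is confirmed later.
4. Require a review, before each escalation, of related grade 3 events that occurred after day 22.

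**Cost.** Escalation becomes easier than under the literal rule: 91% against 71% at the assumed a = b = 0.10. A cohort decision may wait about three weeks when a patient's dose 2 is on hold. Related grade 3 events after day 22 would no longer drive the count. Late esophagitis or pneumonitis could be among them, and Section 4.2.3.1 names these two toxicities for both parts. Step 4 is there for that reason.

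### The 1/6 escalation sentence in section 9.1 has no exception for a level reached by step-down or for the top level, so the text and Table 1 conflict at 70 mg and leave 200 mg unresolved

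*Combined protocol and SAP*

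**What the plan says.** All of this is in section 9.1 (Data Set Descriptions) of the combined protocol and SAP. It applies to Parts A and B, which section 9.0 describes as two independent escalations.

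- Step-down: "If the toxicity is greater than 1/3 in one group then the next lower dose will be used". The next sentence reads "This will establish the MTD, if present".
- Cohort rule: "If one of three patients at any dose level experiences grade 3 or greater toxicity then another 3 patient will be accrued", with the added patients entering that same level. Three outcomes follow. For one patient in six the rule is "If 1/6 patients has grade 3 or higher toxicity then escalation will proceed". For two in six it is "if 2/6 has grade 3 or greater toxicity then this is declared the MTD". For three in six it is "If 3/6 has grade 3 or greater then we will reduce the dose level".
- Table 1 of section 9.1: the row for the 100 mg starting dose gives two destinations, "70mg Q 3 weeks 150mg Q3 weeks", for more than 1/3 and for 0/3 respectively. The 150 mg row is built the same way (down to 100 mg, up to 200 mg). The 70 mg and 200 mg rows list only the outcome of more than 1/3.
- Expansion: "Once the MTD is determined for each study part we will accrue at this MTD until we reach a total of 40 patients" in each part.
- The closing sentence on level +2 says that, with no toxicity so far, enrolment is not closed while the third patient completes the DLT window, because a DLT in that patient would only call for three more patients at the same level.

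Section 4.2.3.1 makes establishing the MTD the purpose of the primary endpoint in both parts.

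**The concern.** A 3+3 rule should give one action for each combination of dose level, route of entry and cohort result. Here the 1/6 sentence takes no account of how the level was reached or whether a higher level exists.

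At the bottom of the ladder this reverses the expected order. At 70 mg, a result of 1/6 reads as grounds to go up, to a dose already exceeded, while the worse result of 2/6 fixes 70 mg as the MTD. At the top, a result of 1/6 asks for a move that cannot be made, and the results that clear 200 mg are never called an MTD.

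The MTD is the main output of both parts, and most patients are enrolled after it is named. If all three upward levels clear, escalation uses 3 × 3 = 9 to 3 × 6 = 18 patients, so 40 − 18 = 22 to 40 − 9 = 31 patients per part enter under an expansion sentence whose trigger has not formally occurred. The rule that stops dosing when DLTs exceed 1/3 is attached to that same expansion cohort. Because the two escalations are independent, the gaps could also be filled differently in Part A and Part B.

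**Working it through.** The documents state no operating characteristic for the escalation, so there is no figure to reproduce. I traced the rules and then sized the two situations.

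**Tracing the wording**

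| Level and result | Cohort rule | Table 1 | Other text in 9.1 |
|---|---|---|---|
| 70 mg, 1/6 | escalate, which means 100 mg | no entry | step-down sentence suggests the MTD is already settled |
| 70 mg, 2/6 | MTD | no entry | – |
| 70 mg, 0/3 | silent | no entry | step-down sentence arguably covers it |
| 100 or 150 mg, 0/3 after step-down | silent | up one level | same sentence points the other way |
| 200 mg, 1/6 | escalate; no higher level | no entry | – |
| 200 mg, 0/3 | silent | no entry | closing sentence implies enrolment stays at 200 mg; no MTD named |

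70 mg can be entered only from 100 mg, after more than 1/3 or at least 3/6 with toxicity there.

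**Probabilities**

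Inputs: cohorts of 3 expanding to 6, and the actions above, all from section 9.1. The per-patient toxicity probability p at each level is an assumption. The values 13% and 32% are borrowed from the background pneumonitis and esophagitis rates in section 4.2.3.1 for illustration only. Results are exact binomial, per part, for the first time through the ladder.

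- P(0/3) = (1−p)³
- P(1/6) = 3p(1−p)² × (1−p)³
- P(pass) = P(0/3) + P(1/6)
- P(exceed) = P(≥2/3) + P(1/3) × P(≥2 of the next 3)

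*Loop at 70 mg* = P(exceed at 100 mg) × P(1/6 at 70 mg).

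With 25% at 70 mg and 40% at 100 mg: P(exceed) = 0.352 + 0.432 × 0.352 = 0.504; P(1/6) = 0.422 × 0.422 = 0.178; product 0.090.

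With 15% and 25%: P(exceed) = 0.156 + 0.422 × 0.156 = 0.222; P(1/6) = 0.325 × 0.614 = 0.200; product 0.044.

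| Assumed rate at 70 / 100 mg | Loop |
|---|---|
| 5% / 5% | 0.1% |
| 10% / 10% | 0.6% |
| 13% / 13% | 1.2% |
| 10% / 15% | 1.4% |
| 20% / 20% | 2.8% |
| 15% / 25% | 4.4% |
| 32% / 32% | 4.9% |
| 20% / 30% | 6.1% |
| 25% / 40% | 9.0% |

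*Top level.* P(1/6 at 200 mg) = P(pass 100) × P(pass 150) × P(1/6 at 200). Replacing the last factor by P(pass 200) adds 0/3.

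- 5% throughout: 0.973² × 0.116 = 0.110; 0.973³ = 0.922.
- 10% throughout: 0.906² × 0.177 = 0.145; 0.906³ = 0.744.
- 10/15/20%: 0.906 × 0.814 × 0.197 = 0.145; 0.906 × 0.814 × 0.709 = 0.523.

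| Assumed rate at 100 / 150 / 200 mg | 1/6 at 200 mg | 0/3 or 1/6 at 200 mg |
|---|---|---|
| 5 / 5 / 5% | 11.0% | 92.2% |
| 10 / 10 / 10% | 14.5% | 74.4% |
| 10 / 15 / 20% | 14.5% | 52.3% |
| 13 / 13 / 13% | 14.1% | 62.0% |
| 20 / 20 / 20% | 9.9% | 35.6% |
| 15 / 20 / 30% | 8.7% | 28.5% |
| 32 / 32 / 32% | 2.9% | 9.4% |
| 30 / 40 / 50% | 0.7% | 2.6% |

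**The case against.** The best defence is that section 9.1 should be read as a whole. It calls the design a standard 3+3, it says that stepping down establishes the MTD, and Table 1 shows no upward move from 70 mg. A competent team would not read the 1/6 sentence as an order to return to an exceeded dose. At the top, 200 mg is the planned ceiling (section 4.2.2 and Table 2), and the closing sentence of 9.1 shows that enrolment is meant to stay there after 0/3.

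Much of this stands, and it rules out several stronger readings:

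- A reader might infer that the protocol directs a return to 100 mg, or re-exposes patients to it. The return is one literal reading of one sentence, contradicted nearby, and each cohort consists of different patients.
- A reader might infer that 0/3 at 70 mg has no outcome. The step-down sentence can be read as making 70 mg the MTD, so I do not count that case as a gap in the figures.
- A reader might infer that the expansion has no dose to use after 0/3 at 200 mg. The closing sentence implies that enrolment stays at 200 mg; what is missing is the MTD declaration.
- A reader might infer that 200 mg would be reported as an MTD that was never reached. Nothing in the documents says so; they are silent on how that result is reported.

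What does not stand is that the general description cures the specific rule. The 1/6 sentence is an express instruction, its scope is express, and Table 1 neither repeats nor overrides it at 70 or 200 mg. Figures in sections 2.1, 2.2 and 9.1 were not visible to me. A schema there might show the intended sequence, but it would not remove the conflict in the wording.

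**Conclusion.** The point holds as a conflict within section 9.1. At 70 mg, the 1/6 sentence disagrees with the step-down sentence and with Table 1, and it treats 1/6 less cautiously than 2/6. Table 1's 0/3 entries at 100 and 150 mg have the same defect after a step-down. At 200 mg, 1/6 has no workable action, and 0/3 has an implied dose but no MTD, although the expansion depends on one.

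The loop at 70 mg is uncommon: about 0.1% to 9% of trials per part, with the upper figure resting on an assumed 40% rate at the starting dose. The clear gap, 1/6 at 200 mg, occurs in about 11% to 15% at 5%, 10% or 10/15/20% by level, and less often at the higher rates shown. The 52% to 92% under those same three assumptions should not be read as the size of the clear gap. It adds the 0/3 case, where only the declaration is missing and staff would probably continue sensibly. All figures rest on assumed rates and treat patients as independent.

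The matter deserves correction because it concerns the rule behind the primary output and the correction is cheap.

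**What to change.** Reconcile the prose of section 9.1, its Table 1 and the expansion sentence into one decision table:

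- one row for each dose level, with separate rows for a level entered by step-down;
- one column for each result (0/3, 1/6, 2/6, at least 3/6, at least 2/3);
- exactly one action in each cell, including the case where the top level is cleared.

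Reword the expansion sentence so that it states which dose is used in every terminal case, and say how the result is reported when no level has been exceeded. Remove or limit any sentence that disagrees with the table. The clinical team decides the action in each cell; this review takes no position on which is right.

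The cost is amendment wording and a fuller table, with no added patients, visits or analyses.

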3.0 OBJECTIVE(S) & HYPOTHESIS(ES)

3.1 Primary Objective(s) & Hypothesis(es)

- (1) **Objective:** Safety of MK 3475 plus chemo/radiation for LS-SCLC and safety of MK 3475 plus radiation for ES-SCLC

Hypothesis: MK-3475 with chemoradiation for LS-SCLC and with radiation for ES-SCLC will demonstrate an acceptable toxicity profile comparable to previous trials

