4.2.3 Rationale for Endpoints

4.2.3.1 Efficacy Endpoints

Part A LS-SCLC: The primary endpoint is safety in order to establish the MTD of MK-3475 with concurrent chemo and radiation. The primary acute toxicity for chemo and radiation is esophagitis with a rate of $\geq 32\%$ ⁸. While the long term toxicity rate of grade 3 pneumonitis is around 13%⁹.

Part B ES-SCLC: The primary endpoint is safety in order to establish the MTD of MK-3475 with concurrent radiation. The primary acute toxicity for chemo and radiation is esophagitis with a rate of $\geq 32\%$ ⁸. While the long term toxicity rate of grade 3 pneumonitis is around 13%⁹.

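### Would the one-third DLT limit in the expansion cohort halt dosing on background esophagitis alone?

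*Combined protocol and SAP*

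**What the plan says.** Section 9.1 runs a 3+3 escalation in each part and then expands: "we will accrue at this MTD until we reach a total of 40 patients for each study part". For that stage it adds one numeric limit: "Should DLTs occur in more than 1/3 of patients enrolled into this expanded cohort, dosing at that level will be stopped". After a crossing the DLTs are reviewed, and whether to lower the dose is decided by agreement between the IRB and the investigator. The section gives no first check, no look schedule and no operating characteristics for the limit.

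The DLT definition, also in 9.1, opens with attribution: "DLTs are defined as any adverse event(s) considered related to the combination of MK-3475 plus radiation as described below". One item, at that grade or higher, is any other "Grade 3 non-skin related adverse event with the exception of laboratory abnormalities". Esophagitis is not exempted. On timing: "The time frame for DLT assessment will be within 22 days of therapy initiation". A further item is "Drug related toxicity that prevents administration of MK-3475 for > 21 days from the scheduled dose".

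Section 4.2.3.1 says for both parts: "The primary acute toxicity for chemo and radiation is esophagitis with a rate of" 32% or more. No grade or period is attached to that figure. The hypothesis in 3.1 is that the combination "will demonstrate an acceptable toxicity profile comparable to previous trials".

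**The concern.** The limit and the quoted background almost coincide. If MK-3475 adds nothing, which is what the hypothesis in 3.1 amounts to, and if all background esophagitis counts, the expected DLT proportion lies just under the stopping line. Chance alone would then carry many cohorts over it. The rule covers 22 to 34 of the 40 patients in each part, depending on the escalation path, and it bears on the primary endpoint. Because the plan does not say when the proportion is read, or how to treat an event that radiation alone would explain, a reader cannot tell from the text how likely a false alarm is.

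**Working it through.** **The plan's own figure.** There is none for this rule. The nearest is the 88% in 9.2.5 for seeing at least one toxicity among 40 patients at a true rate of 0.1. The formula gives 1 − 0.9^40 = 0.985; 88% is the value for 20 patients (1 − 0.9^20 = 0.878). That is a different question and does not enter below.

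**Inputs.**
- Limit: dosing stops when 3 × DLTs > n (9.1).
- Expansion size: 34 of the 40, the largest case (6 treated beforehand).
- Background: 32% (4.2.3.1). The share that is Grade 3 or higher, inside 22 days and judged related is not given. I assume 25%, 50%, 75% or 100%, which gives DLT rates p of 0.32 × 0.25 = 8%, 16%, 24% and 32%.

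**One check at the end.** 3X > 34 means X ≥ 12. P(X ≥ 12 | n = 34, p) is under 0.1% at 8%, 0.5% at 16%, 9% at 24% and 40% at 32%.

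**Repeated checks.** Let f(n, x) be the probability of x DLTs in n patients without an earlier crossing. Then f(n, x) = (1 − p) f(n − 1, x) + p f(n − 1, x − 1). At each check, all probability with 3x > n moves to stopped.

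| True DLT rate | End only | Every 10 and end | Each patient from 10th | From 6th | From 3rd | From 1st |
|---|---|---|---|---|---|---|
| 8% | <0.1% | 1% | 1% | 2% | 6% | 17% |
| 16% | 0.5% | 8% | 11% | 16% | 24% | 38% |
| 24% | 9% | 29% | 38% | 43% | 51% | 62% |
| 32% | 40% | 62% | 70% | 74% | 78% | 83% |
| 40% | 77% | 87% | 91% | 92% | 94% | 95% |

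**The right-hand column.** Read from the first patient, one DLT in the first two patients crosses the limit (1/1 or 1/2). That alone has probability 1 − (1 − p)², which is 1 − 0.92² = 15% of the 17% at p = 8%, and 1 − 0.68² = 54% of the 83% at p = 32%. Section 9.1 itself answers one event in three by treating three more patients, so reading a proportion off one or two patients is not a natural use of the rule.

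**Pooling the dose-finding patients.** The text names the expanded cohort, so the table leaves them out. If they are included after entry at 1/6 with 31 expansion patients, dosing stops when 3(x + 1) > n + 6. Continuous checking then gives 1%, 7%, 25% and 54% at the four rates. One end check at 32% gives 27%.

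**What a slower rule costs.** At a true 40%, the mean number of expansion patients treated is 8.4 (checks from the 3rd), 11.0 (from the 6th), 13.8 (pooled) and 15.7 to 17.3 (pooled, first check at 12). At 50% the figures are 5.2, 7.7, 8.3 and 10.4 to 12.3.

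**The case for a change.** The best case for acting has four parts. First, the 32% is written as a lower bound, and Part A radiation runs over 15 days, so much esophagitis could fall inside the 22-day window if radiation and MK-3475 start together. Second, a rule meant to protect patients has to be read during accrual, so the 40% from one end check is a generous floor; with all of the 32% counted, the repeated-check readings in the table give 62% to 83%. Third, no sentence says how to attribute an event that radiation alone would explain. Fourth, a clarifying line and a small table would cost little.

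The first two points stand as arithmetic, but only if the whole 32% is a DLT rate. The plan does not say that it is, and the result falls steeply as the share falls. The figure is also quoted for chemo and radiation, while Part B has no concurrent chemotherapy, so it is weaker there. The third point is narrower than it looks. Table 10 in 7.2.4 guides causality, asks whether another cause reasonably explains the event, and answers no where another cause is obvious. It is written for the Merck product rather than for the combination with radiation, so investigators must carry it across. On the fourth, the table would rest on a background share that the documents do not supply, and the choices behind it (what counts, when to look, whether to pool) all carry costs. Leaving expected esophagitis out could hide a worsening caused by MK-3475; counting it brings the false alarms above.

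A side point is correct but separate. The item on MK-3475 being prevented for more than 21 days cannot be met for the second dose until more than 21 + 21 = 42 days after initiation, which does not fit a 22-day window. The two lines have to be reconciled when DLTs are adjudicated. The item does not drive the esophagitis result.

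**Conclusion.** No change to the plan follows. The limit does lie next to the quoted background, and the plan is silent on look times and on expected radiation events. The alarming probabilities, 40% to 83% with 34 expansion patients and no pooling, need the extreme assumption that every background esophagitis case is a related, Grade 3 or higher event within 22 days. At half that rate the range is 0.5% to 38%, and at a quarter it is under 0.1% to 17%; in both, the top end comes from judging a proportion on the first one or two patients.

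The limit agrees with the tolerance used in escalation, where 2/6 is declared the MTD. The same DLT definition will already have been applied to at least 6 patients (40 − 34) before expansion opens, so the team will have met the attribution question by then. A crossing is not free, since dosing at that level stops, but it leads to a case-by-case review and not to automatic closure. That review can set the events against the esophagitis and pneumonitis rates in 4.2.3.1. What remains is operating detail that the team can fill in, with a real trade-off between false alarms and speed of detection and no single setting that is plainly better.
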